6.10. Concomitant and Prior Therapy

Concomitant medications will be summarized and compared between treatment groups using Prescott's exact test for the Randomized Population during the 2 randomized treatment periods (Period I and Period II). The percentages of patients receiving each concomitant medication will be summarized by treatment using preferred term nested within Anatomical Therapeutic Chemical (ATC) Level 3 code. Medications will be ordered by decreasing frequency within ATC level. Concomitant medication used during the lead-in period will also be summarized for the Enrolled Population.

A summary of previous diabetes therapies that were discontinued prior to informed consent will be generated for the Enrolled Population.

The daily basal dose, daily bolus dose, total insulin dose, and the ratio of bolus dose to total insulin dose during the lead-in period will be summarized by visit for overall and by treatment sequence. The doses and bolus/total insulin dose ratios for each visit will be calculated as the mean of the doses for the last 3 days prior to the visit date that are entered in the eCRF. Doses will be summarized in U and U/kg.

6.11. Safety Analyses

6.11.1. Primary Outcome and Methodology

The primary objective of this study is to compare LY900014 and insulin lispro with respect to the rate (events/patient/30 days) of infusion set failures that lead to premature infusion set changes, due to a pump occlusion alarm OR due to unexplained hyperglycemia with blood glucose (SMBG) >250 mg/dL (13.9 mmol/L) that does not decrease within 1 hour following a correction bolus delivered via the pump, during the 6-week treatment period.

To be considered as the primary endpoint, an infusion set failure must result in a premature infusion set change due to:

1. pump occlusion alarm(s), OR
2. unexplained hyperglycemia that meets the following conditions:
 - Associated with a non-meal-related correction bolus delivered via the pump at least 1 hour before the infusion set change
 - Most recent self-monitored blood glucose (SMBG) within 1 hour before the correction bolus >250 mg/dL (13.9 mmol/L)
 - At least 1 SMBG obtained following the correction bolus prior to the infusion set change
 - Within 1 hour (+10 minutes) following the correction bolus, the most recent SMBG prior to the infusion set change does not indicate a decrease in blood glucose

If more than 1 non-meal-related correction bolus is given for an unexplained hyperglycemia, only the first correction bolus time will be used to determine the 1 hour (+10 minutes) timeframe following the correction bolus as described in Section 9.1.4.1.2 of the protocol.

For each treatment period (lead-in, Period I and Period II), the infusion set failure rate (events/patient/30 days) will be calculated for each patient as the total number of events while the patient is on pump and on study treatment divided by the days of exposure [last dose date and time – first dose date and time – duration of pump or treatment interruption] times 30.

The analyses of the primary objective will be conducted on the Safety Population including data collected prior to permanent discontinuation of investigational product (i.e., last dose) in each randomized treatment period (Period I and Period II) and excluding data (if any) that are collected while patients temporarily are off pump or off IP. Treatment group comparisons will be performed using Wilcoxon signed-rank test at the full significance level of 0.05, with patients who are dosed in both treatment periods.

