#### **9.1.4.1.2. Infusion Set Changes**

The eCOA system will be used by patients to collect all infusion set changes, including date and time of change, designation of routine or premature change, primary reason for premature change (infusion set kinked, came out, or leaking; empty pump reservoir; infusion site pain or redness; pump occlusion alarm; suspected infusion set occlusion; other).

In the case of suspected infusion set occlusion, patients will choose or enter a new correction bolus from the eCOA diary that corresponds to the time of the suspected occlusion. They will then indicate if the correction bolus was given via pump or via syringe. If more than one correction bolus is given, patients should choose the first non-meal related correction bolus. This information is also critical in order to evaluate the primary objective of the study.

Investigators will review pump occlusion alarms, suspected infusion set occlusions, and premature infusion set changes with patients at each visit.

Any interruption of CSII will need to be documented in the eCRF. When patients resume use of pump following the interruption, the infusion set insertion should be entered as “routine” infusion set change in eCOA.

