^a In extremely rare cases where patients stopped treatment on pump but continued to use treatment through syringe until they discontinue from the study, the last dose form will capture the timing of the last dose of treatment in CRF, which will not be the last infusion set change.

The last infusion set change in each treatment period (lead-in, Period I or Period II) occurs only when a patient comes to an office visit or early discontinuation of study treatment. This change is not reflective of patients' behavior regarding infusion set changes, and thus it will not be included in the derivation of time until infusion set changes. Patient-reported premature infusion set changes due to the reason "Other" or patient-reported routine infusion set changes that occur within 1 hour of a previous infusion set change (captured in the case report form [CRF]), will be treated as a redundant entry in eCOA and excluded from all analyses. In addition, any patient-reported routine infusion set change that occurred within 24 hours of a previous infusion set change could have been misreported as routine or are redundant entries in eCOA, and thus will be excluded from all analyses.

Time interval until infusion set change for each infusion set can be derived through a minute-to-day conversion by dividing the time difference between the infusion set change and its previous infusion set change by 1440 minutes. The protocol requires that patients change infusion set every 72 ± 4 hours unless a change is required for failure of the infusion set. To handle potential missing input in eCOA for the infusion set change, time interval until infusion set change greater than 7 days (168 hours) will be excluded. For each treatment period, time interval until infusion set change will be derived by averaging all infusion set changes within the period. The analyses will be conducted by an MMRM model (Model 2) as specified in Section 6.1.

Derivation and analysis of interstitial glucose reduction rate are described in Section 6.12.

Actual and change from baseline in total, basal, and bolus insulin doses and bolus/total insulin dose ratios will be compared between LY900014 and insulin lispro using an MMRM model (Model 1) as specified in Section 6.1. The doses and bolus/total insulin dose ratios for each visit will be calculated as the mean of the doses for the last 3 days prior to the visit. A listing of insulin doses will also be provided, including data collected at Visit 801.

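### The unexplained-hyperglycemia limb of the primary endpoint can count a second set change on a correction bolus that went through the previous set

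*SAP*

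**What the plan says.** SAP 6.11.1, matched by Protocol 10.3.3.1 and the Synopsis, gives two routes to a primary event: an occlusion alarm, or unexplained hyperglycemia meeting four conditions.

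- Bolus: the change must be "Associated with a non-meal-related correction bolus delivered via the pump at least 1 hour before the infusion set change".
- Starting glucose: the latest self-monitored value in the hour before that bolus is above 250 mg/dL.
- Follow-up value: "At least 1 SMBG obtained following the correction bolus prior to the infusion set change".
- Response: within 1 hour (+10 minutes) of the bolus, "the most recent SMBG prior to the infusion set change does not indicate a decrease in blood glucose".

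Where several boluses are given for one unexplained hyperglycemia, "only the first correction bolus time will be used to determine the 1 hour (+10 minutes) timeframe following the correction bolus".

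Protocol 9.1.4.1.2 and SAP 5.1 describe how the bolus is linked. For a suspected occlusion, "patients will choose or enter a new correction bolus from the eCOA diary that corresponds to the time of the suspected occlusion", and the patient states whether it was given by pump or syringe. Then: "If more than one correction bolus is given, patients should choose the first non-meal related correction bolus".

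SAP 6.11.2 removes some entries as redundant or misreported: changes reported as routine or for the reason Other within 1 hour of a previous change recorded in the case report form, and routine changes within 24 hours of a previous change. Changes reported as suspected occlusion are not covered.

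**The concern.** The endpoint is meant to count failures of infusion sets, so the evidence for a failure should come from insulin delivered through the set being removed. The conditions set a minimum gap between bolus and change but no maximum, and none refers to when the removed set was inserted. The first-bolus rule does not restart at a set change, and the documents do not say when one unexplained hyperglycemia ends and another begins.

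A second change in the same hyperglycemia can therefore be judged on a bolus that never passed through the second set. At stake are the primary rate, the attribution of events to sets, and the dwell-time table in SAP 6.11.2: a set removed soon after insertion falls in its class of 24 hours or less, so false events would collect there. The trial claims no power for non-inferiority or superiority (SAP 5.2), so the estimated rates carry much of its message.

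**Working it through.** **The plan's own figure.** The sample-size sections state 48 randomized for about 42 completers at 12% dropout: 42 / (1 − 0.12) = 47.7, rounded up to 48. It reproduces, and nothing below depends on its accuracy. The current text gives no event rate.

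**Applying the conditions literally.** The records are invented. Times are minutes from the first pump bolus, which goes through set A. Glucose is in mg/dL and is 300 at −5 in every record. Both changes are reported as suspected occlusion in one hyperglycemia, and the first bolus is used for the count as written.

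| Record | Later glucose | Set changes | Pump bolus through B | Events as written | Events with insertion condition |
|---|---|---|---|---|---|
| 1 | 310 at 60 and 70; 255 at 135 | A just after 70; B at 150 | at 75 | 2 | 1 |
| 2 | 310 at 60 and 70 | A at 75; B at 95 | none | 2 | 1 |
| 3 | 305 at 35; 302 at 65 | A at 40; B at 90 | none | 1 (set B) | 0 |
| 4 | 310 at 60 and 70; 320 at 140 | A just after 70; B at 150 | at 75 | 2 | 2 |

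- Record 1, set B as written: the bolus at 0 is 150 minutes before the change, the starting value is 300, a later value exists, and the last value in the 70-minute window is 310, which is no decrease. Set B counts, although 310 was measured on set A and glucose then fell to 255 on set B. If the patient links the bolus at 75 instead, the comparison is 310 to 255 and set B does not count.
- Record 3: set A was changed 40 minutes after the bolus, so it fails the 1-hour condition. Set B then counts on a bolus given through set A. Here incidence can change as well as rate.
- Record 4: set B also fails on its own bolus, so both rules give two events.

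**Size of one miscounted event.**

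- Patient-period rate: 1 / 42 days × 30 = 0.71 events/30 days.
- Mean over 42 patients: 0.714 / 42 = 0.017 events/30 days.
- Against assumed rates of 0.10 to 0.44 events/patient/30 days: 42 × 42/30 × 0.10 = 5.9 events per insulin, and × 0.44 = 25.9. One event is then about 17% or 4% of the total. The 0.10 is an assumption. The 0.44 appears only in superseded text in Protocol Appendix 8, for a different definition (above 300 mg/dL, no fall of more than 50 mg/dL, no alarm limb), and serves here only as an upper value.

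**Effect on rate and test.** If a share q of events is followed by a miscounted second change, a rate r becomes r(1 + q). A simulation used 42 pairs, 4000 runs per scenario, Poisson counts with a gamma patient effect shared by both periods, equal true rates and a two-sided signed-rank test at 0.05. The shares are assumptions. Every event was treated as a hyperglycemia event and every second change as false, which overstates the effect.

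| Share on each insulin | Rejection, r = 0.10 | Rejection, r = 0.44 |
|---|---|---|
| 0% / 0% | 0.038 | 0.050 |
| 10% / 10% | 0.044 | 0.050 |
| 30% / 30% | 0.040 | 0.052 |
| 10% / 0% | 0.045 | 0.060 |
| 30% / 10% | 0.052 | 0.070 |

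Mean rates rise to about 0.11 and 0.48 at a 10% share, and to about 0.13 and 0.58 at 30%.

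**The case against.** The strongest reply is that the diary already ties the bolus to the right occlusion. Patients are asked for the bolus matching the time of the suspected occlusion, and the first-bolus sentence can be read as choosing among boluses for that occlusion, not as reaching back to a set already removed. A patient who links the second set's own bolus, or a syringe dose, produces no miscount. High glucose left over after a recognized first failure is also arguably no longer unexplained, although Protocol Appendix 1 does not name occlusion among its explanations. The reporting flow chart (SAP Figure ITSI.5.2) is not visible here and may settle some of this. Unexplained hyperglycemia is expected to be uncommon (Protocol 5.1), the rule is applied blind to both insulins, and the SAP 6.11.2 listings would expose repeat changes.

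Much of this stands. It makes the miscount conditional and probably rare. It does not remove it: the linking text refers to time rather than to a set, the next instruction points to the first bolus, and the SAP algorithm uses that bolus without checking insertion time. A patient following the instructions can produce record 1. The listings show the problem but do not correct the count.

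A reader might infer that every second change in an episode is counted wrongly. The documents do not support that: it must be reported as suspected occlusion, be treated as the same hyperglycemia and be tied to the earlier bolus, and a genuine second failure (record 4) is a valid event.

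**Conclusion.** The gap is real and worth closing before unblinding. Under the stated rule, a second set change in one hyperglycemia can be counted on the previous set's response, or counted when the first change did not qualify. Each such event adds 0.71 events/30 days to a patient-period and 0.017 to a 42-patient mean. The harm is to the rate estimate, to event attribution and to the dwell-time class of 24 hours or less. Incidence changes only in cases like record 3, and then only if the patient has no other event in that period.

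Two stronger conclusions are tempting. One is that the primary rate is overstated by some stated percentage; the documents give no frequency of repeat changes, so any percentage is an assumption. The other is that the primary test is compromised. In the simulation the rejection rate stayed at 0.04 to 0.05 with equal shares, and reached only 0.07 with an arbitrary 30% against 10% at the higher assumed rate.

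**What to change.** Add one condition to SAP 6.11.1 and align Protocol 10.3.3.1: the linked, pump-delivered bolus and the response glucose must both be later than the insertion time of the set being changed, and the first-bolus rule restarts at each set insertion. A change whose linked bolus precedes that insertion is not a hyperglycemia-limb event, but it stays in the by-reason counts.

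Do not substitute an unlinked bolus from the diary log in the primary count. Protocol 9.1.4.1.1 asks for date, time and dose, and route is asked only for the linked bolus (9.1.4.1.2, 9.4.7), so an unlinked syringe dose could pass for a pump bolus through the new set. Use such boluses only in a sensitivity analysis, under the pump-delivery presumption already in SAP Table ITSI.6.8, note 4. List every reclassified change, and report the count under the present rule as a further sensitivity analysis.

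The cost is a sentence of SAP text with its protocol counterpart, a programming condition, a listing and two sensitivity counts. Set-change and bolus times are already collected. The downside is that a few genuine second-set failures, corrected by syringe or linked to the earlier bolus, leave the primary count; the listing keeps them visible.

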## 10. Statistical Considerations

### 10.1. Sample Size Determination

Approximately 48 patients (24 patients in each treatment sequence) will be randomized in order that approximately 42 patients complete the study.

The primary objective of this study is to compare LY900014 and insulin lispro with respect to the rate (events/patient/30 days) of infusion set failures that lead to premature infusion set changes, due to a pump occlusion alarm OR due to unexplained hyperglycemia with blood glucose (SMBG) >250 mg/dL (13.9 mmol/L) that does not decrease within 1 hour following a correction bolus delivered via the pump during the 6-week treatment period.

The study was designed following a regulatory interaction to assess the safety comparability of LY900014 and insulin lispro. It is not designed or powered to be a non-inferiority or superiority trial.

Assuming a 12% dropout rate after randomization, approximately 48 patients (24 patients in each treatment sequence) will need to be randomized.

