### 10.3.3. Safety Analyses

#### 10.3.3.1. Primary Analyses

The primary objective of this study is to compare LY900014 and insulin lispro with respect to the rate (events/patient/30 days) of infusion set failures that lead to premature infusion set changes, due to a pump occlusion alarm OR due to unexplained hyperglycemia with blood glucose (SMBG) >250 mg/dL (13.9 mmol/L) that does not decrease within 1 hour following a correction bolus delivered via the pump, during the 6-week treatment period.

To be considered as the primary endpoint, an infusion set failure must result in a premature infusion set change due to:

1. pump occlusion alarm(s), OR
2. unexplained hyperglycemia that meets the following conditions:
  - Associated with a non-meal-related correction bolus delivered via the pump at least 1 hour before the infusion set change
  - Most recent self-monitored blood glucose (SMBG) within 1 hour before the correction bolus >250 mg/dL (13.9 mmol/L)
  - At least 1 SMBG obtained following the correction bolus prior to the infusion set change
  - Within 1 hour (+10 minutes) following the correction bolus, the most recent SMBG prior to the infusion set change does not indicate a decrease in blood glucose

If more than 1 non-meal-related correction bolus is given for an unexplained hyperglycemia, only the first correction bolus time will be used to determine the 1 hour (+10 minutes) timeframe following the correction bolus as described in Section [\(9.1.4.1.1\)](#).

The infusion set failure rate (events/patient/30 days) will be derived for each patient for the lead-in, Period I, and Period II, and summarized by treatment sequence.

The analyses of the primary objective will be conducted on the Safety Population including data collected prior to permanent discontinuation of investigational product (i.e., last dose) in each randomized treatment period (Period I and Period II) and excluding data (if any) that are collected while patients temporarily are off pump or off IP. Treatment group comparisons will be performed using Wilcoxon signed-rank test at the full significance level of 0.05, with patients who are dosed in both treatment periods.

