5.2. Determination of Sample Size

Approximately 48 patients (24 patients in each treatment sequence) will be randomized in order that approximately 42 patients complete the study.

The primary objective of this study is to compare LY900014 and insulin lispro with respect to the rate (events/patient/30 days) of infusion set failures that lead to premature infusion set changes, due to a pump occlusion alarm OR due to unexplained hyperglycemia with blood

glucose (SMBG) >250 mg/dL (13.9 mmol/L) that does not decrease within 1 hour following a correction bolus delivered via the pump, during the 6-week treatment period.

The study was designed following a regulatory interaction to assess the safety comparability of LY900014 and insulin lispro. It is not designed or powered to be a non-inferiority or superiority trial.

Assuming a 12% dropout rate after randomization, approximately 48 patients (24 patients in each treatment sequence) will need to be randomized.

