Unless otherwise noted, all tests of treatment effects will be conducted at a 2-sided alpha level of 0.05, and confidence intervals (CIs) will be calculated at 95%, 2-sided. If conducted, all tests of interactions between treatment groups and other factors will be conducted at a 2-sided alpha level of 0.10.

The definitions of baseline and post-baseline for the safety and efficacy analyses depend on which analysis period is being used. The following analysis periods will be used:

- Lead-in Period – Visits 2-3
- 12-Week Treatment Period while on IP – from first dose to last dose of IP in each 6-week randomized treatment period (Period I and Period II)
- 12-Week Treatment Period Regardless of IP use – from randomization to Week 6 of each randomized treatment period (including all data regardless of IP use)
- Safety Follow-up Period – Visit 801

Table ITSI.6.2 describes the rules for determining the patient population, baseline and postbaseline observations for the different analysis periods. The data in the lead-in and the safety follow-up visit, if summarized, will be for overall, not by treatment group.

The data on IP is defined based on the following rules:

- for data only measured at an office visit (for example, HbA1c), if the office visit date (or laboratory sample collection date) is within 14 days of the date of last study drug dose of the randomized treatment period (Period I or Period II), then postbaseline data measured at or prior to that office visit will be considered as data on IP.
- for data collected as running records with an exact date and/or time stamp such as diary entries where the date and time of the measures was not tied with the date of an office visit, postbaseline data with date and time \leq (last study drug dose date and time) will be considered as data on IP.

For continuous measures, summary statistics will include sample size, mean, standard deviation (SD), median, minimum, and maximum for both the actual and the change from baseline measurements. Least squares (LS) means and standard errors derived from the analysis models will also be displayed for the change from baseline measurements. Treatment comparisons will be displayed showing the treatment difference LS means and the 95% CIs for the treatment differences, along with the p-values for the treatment comparisons.

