6.11.2. Other Secondary Safety Analyses

The analyses described in Section 6.11.2 will include data collected for the Safety Population including data collected prior to permanent discontinuation (i.e., last dose) of IP in each 6-week treatment period. In addition, other than severe hypoglycemia events, all secondary safety endpoints are pump-related, and therefore the corresponding analyses will also exclude data (if any) that are collected while patients temporarily are off pump or off IP.

For the following secondary safety endpoints, the incidence (percent of patients with at least 1 event) and rate will be analyzed using Prescott's exact test and Wilcoxon signed-rank test, respectively, as described above for the primary endpoint.

- suspected infusion set occlusions defined as unexplained hyperglycemia with blood glucose (SMBG) >250 mg/dL (13.9 mmol/L) that does not decrease within 1 hour (+10 minutes) following a correction bolus delivered via the pump and that leads to an infusion set change
- infusion set failures leading to premature infusion set changes due to unexplained hyperglycemia with blood glucose >250 mg/dL that does not decrease by >50 mg/dL within 1 hour (+10 minutes) following a correction bolus delivered via the pump
- premature infusion set changes for any reason and for each individual reason (infusion set kinked, came out or leaking; empty pump reservoir; infusion site pain or redness; pump occlusion alarm; suspected infusion set occlusion; other)
- severe hypoglycemic events

For the infusion set failures and premature infusion set changes, the number of events and the number of patients with events will be derived for each treatment group by infusion set catheter dwell time (≤ 24 hours, >24 and ≤ 48 hours, >48 and ≤ 72 hour, >72 hours), and overall (across over the course of approximately 72-hours of continuous infusion).

A listing of premature infusion set changes due to unexplained hyperglycemia will be generated. For each premature infusion set change due to unexplained hyperglycemia, the following information will be provided:

- whether it is an infusion set failure that meets the primary endpoint definition

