6.11.4. Extent of Exposure

Duration of exposure to study drug will be summarized. The following summary statistics will be provided: n, mean, SD, median, minimum, maximum, and sum (that is, total patient-years of exposure). The number and proportion of patients falling into the following different exposure categories will also be summarized: <7 days (>0 and <7 days), ≥ 7 and <14 days, ≥ 14 and <28 days, ≥ 28 days and < 42 days) and ≥ 42 days.

Patients who complete the study treatment period are required to complete a safety follow-up visit without study drug; and patients who discontinue the IP prematurely are required to discontinue from the study (ITSI Protocol 8.1-8.2).

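### The primary infusion-set-failure rate is compared by a signed-rank p-value only, with no planned rate ratio or difference and confidence interval, although the aim is safety comparability

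*SAP*

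**What the plan says.** SAP 6.11.1 computes the rate for each patient and period as "total number of events while the patient is on pump and on study treatment divided by the days of exposure", net of interruptions, times 30. Treatments are then compared "using Wilcoxon signed-rank test at the full significance level of 0.05, with patients who are dosed in both treatment periods". Protocol 10.3.3.1 plans the same test and adds that rates are "derived for each patient for the lead-in, Period I, and Period II, and summarized by treatment sequence".

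SAP 6.1 sets 95% two-sided as the general interval level. For continuous measures it says: "Treatment comparisons will be displayed showing the treatment difference LS means and the 95% CIs for the treatment differences". Protocol 10.3.1 has the same rule, and in both documents the least squares means come from the analysis models.

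Other planned outputs touch the endpoint. Protocol 10.3.3.2 compares incidence with Prescott's exact test. In SAP 6.11.2, "the number of events and the number of patients with events will be derived for each treatment group by infusion set catheter dwell time", and also overall. SAP 6.11.4 summarizes exposure, including the "sum (that is, total patient-years of exposure").

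On purpose, SAP 5.2 says the study was designed "to assess the safety comparability of LY900014 and insulin lispro". Protocol 10.1 gives the same aim and adds: "It is not designed or powered to be a non-inferiority or superiority trial".

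**The concern.** A comparability aim asks how much worse the new product could be, given the data. A signed-rank p-value does not answer that; an interval for a ratio or difference does, and it needs no margin. Neither document says comparability will be concluded from p>0.05, but neither says what else would support it. Without a planned estimator, the report must either lean on a non-significant test from a study that disclaims power, or choose an estimator after the results are known.

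**Working it through.** **Step 1. Does any planned output give a treatment contrast with an interval for the primary rate?**

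| Planned output | What it gives | Contrast with interval? |
|---|---|---|
| Signed-rank test (SAP 6.11.1, Protocol 10.3.3.1) | p-value | No |
| Rates by sequence and period (Protocol 10.3.3.1) | Descriptive rates; each sequence-period cell is one treatment | No |
| LS mean differences (SAP 6.1, Protocol 10.3.1) | Model-based differences with 95% CI | Not for this rate, which has no model |
| Prescott's test on incidence (Protocol 10.3.3.2) | p-value | No |
| Counts by dwell time and overall (SAP 6.11.2) | Events and patients with events | No |
| Exposure (SAP 6.11.4) | Total exposure | No |
| Time until infusion set change, MMRM Model 2 (SAP 6.11.2) | Difference with 95% CI | Yes, but for another endpoint |

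**Step 2. The plan's own figure.** About 42 completers with 12% dropout: 42 / (1 − 0.12) = 47.7, rounded up to 48. This reproduces and is not in dispute.

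**Step 3. Inputs for an illustration.** The current text gives no event rate. The rate 0.44 per 30 days and dispersion 0.29 appear only in the superseded power statement logged in Protocol Appendix 8, for a different endpoint definition. The rates 0.10 and 0.20 are assumptions. Dispersion is read as a gamma variance of 0.29 or 1/0.29 = 3.45, with patient effects shared by both periods or independent.

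**Step 4. Hand check at a true ratio of 1.** Expected events per treatment = rate × (42 days / 30) × 42 patients. Ignoring overdispersion, SE(log ratio) = √(1/E + 1/E), and the upper limit is exp(1.96 × SE).

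- 0.10: E = 5.9, SE = 0.583, upper limit 3.1
- 0.20: E = 11.8, SE = 0.412, upper limit 2.2
- 0.44: E = 25.9, SE = 0.278, upper limit 1.7

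**Step 5. Simulation with overdispersion.** Gamma-Poisson counts, 39 to 45 days per period, 2,000 trials per cell. The signed-rank test is applied to rate differences with zeros dropped. The ratio comes from a Poisson GEE with treatment, period and log-exposure offset, Mancl-DeRouen standard error, and t with N − 3 df. The table takes 48 randomized, 3 dosed in Period I only and 3 stopping in Period II.

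| Quantity | Lispro rate | 0.29 shared | 0.29 indep. | 3.45 shared | 3.45 indep. |
|---|---|---|---|---|---|
| Power, true ratio 2 | 0.10 | 24.1% | 24.4% | 20.8% | 14.6% |
| | 0.20 | 48.2% | 43.6% | 41.7% | 20.6% |
| | 0.44 | 80.7% | 73.0% | 71.7% | 26.9% |
| Median upper limit, true ratio 1 | 0.10 | 3.32 | 3.40 | 3.07 | 4.04 |
| | 0.20 | 2.27 | 2.38 | 2.19 | 2.98 |
| | 0.44 | 1.76 | 1.85 | 1.72 | 2.54 |
| Upper limit <2, given true ratio 1 and p≥0.05 | 0.10 | 18% | 17% | 23% | 14% |
| | 0.20 | 37% | 33% | 41% | 24% |
| | 0.44 | 69% | 60% | 67% | 29% |

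Two other layouts were run: 6 patients in Period I only, and 42 full pairs. Across all three, at 0.10, 0.20 and 0.44:

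- power for a doubling is 14–24%, 20–48% and 25–81%;
- the median upper limit under equality is 3.1–4.5, 2.2–3.1 and 1.7–2.7;
- among equal-rate trials with p≥0.05, the upper limit is below 2 in 12–23%, 22–41% and 26–69%.

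Among true-doubling trials with p≥0.05, the upper limit is 2 or more in 88–98%. Signed-rank type I error is 2.5–6.5%.

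**Step 6. Cross-checks.** Another simulation with 42 pairs of 42 days each gave power for a doubling of 16–28% at 0.10 and 25–81% at 0.44. Its expected upper limits under equality were about 3.5–5.6 and 1.75–2.70. The superseded claim of at least 80% power (0.44 against 2.0, 42 pairs) is met closely only under 3.45 with independent periods (80.8%); the other three readings give 100%. In that reading, power for a doubling at 0.44 is 25–27% and the median upper limit is 2.5–2.7.

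**The case against.** The strongest reply has four parts.

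- **The gap is narrow.** Rates by sequence and period identify the treatment in each cell, so a crude difference can be read off. SAP 6.1 shows intervals are the default elsewhere, and time until infusion set change has one. All true, but a crude difference has no stated uncertainty, the default names no estimator for this rate, and time to change averages routine and premature changes.
- **The plan does not overclaim.** It openly disclaims non-inferiority, superiority and power, and cites a regulatory interaction whose content cannot be seen. This stands: the lack of a margin or power is disclosed and is not the defect. An interval needs neither.
- **The numbers are soft.** They rest on superseded or assumed rates, span a wide range, and are not bounds. A CI does not raise power. This also stands, so they are an illustration only. The textual gap does not depend on them.
- **The estimator is a preference.** A GEE ratio uses a different estimand, a period term and more patients than the test. It disagrees with the test on significance in 8–18% of true-doubling trials and 2–5% of equal-rate trials. SAP Version 3 moved hypoglycemia rates to the signed-rank test because of convergence problems. A paired rate difference is a reasonable alternative, but it too disagrees with the test in 5–10% of true-doubling trials. The choice is one of form.

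SAP 6.1 already permits additional exploratory analyses, so an interval could be reported anyway. One named before unblinding carries more weight than one chosen afterwards.

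**Conclusion.** The concern holds. The only planned between-treatment inference on the primary rate is a p-value, and no general rule in either document supplies an interval for it. Followed as written, the plan cannot state which increases in failures are excluded, which is what a comparability aim needs. This is an omission in the analysis plan, not an error or bias in the signed-rank test or the sample size.

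The practical size depends on the event rate, which the current documents do not give. At assumed rates of 0.10 and 0.20, a doubling would usually be missed and would usually remain inside the interval when the products are equal. At 0.44 the answer turns on dispersion and on how patient effects carry across periods.

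A minor point: patients dosed only in Period I, at most about 48 − 42 = 6, fall outside the paired test. An estimate on the full Safety Population would include them.

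**What to change.** Keep the signed-rank test as the primary test. Add to SAP 6.11.1, before unblinding, a supportive treatment effect for the exposure-adjusted failure rate on the Safety Population, with a 95% CI. One option is a log-link Poisson GEE rate ratio (LY900014 to lispro), with log days on pump and on IP as offset, treatment and period as fixed effects, patient as cluster, and a small-sample standard error.

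Name a fallback for non-estimable cases: events, exposure days and rate per treatment, with a rate difference and a patient-level bootstrap interval. State that the interval is reported beside the p-value, that both are shown if they disagree, and that p>0.05 alone is not read as evidence of comparability.

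The cost is one extra analysis on data already collected, with no new patients, visits or alpha. Because the primary test keeps its role, it fits the rule in Protocol 10.3.1 and SAP 6.1 that only a change to a principal feature needs an amendment. With sparse events the interval is approximate: simulated coverage was 92.6–98.1%, and the ratio was not estimable in 0–3.1% of trials.
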